11.3.4.3. Data Reporting and Electronic Case Report Forms

The Investigator and/or designee will accurately, completely, and in a timely manner enter data resulting from execution of the protocol into eCRFs. One eCRF will be completed for each participant and must be electronically signed and dated by the Principal Investigator responsible for participant care during the study. The EDC system audit trail captures all eCRF data related activities such as: data entry, data modifications, data verification, data lock, e-signature etc. At the end of the study, each site will be given an electronic copy of all study data entered in the eCRF plus external data. eCRF data will be extracted from the EDC system into SAS® datasets on a periodic basis and at defined study timepoints for statistical analysis.

11.3.4.4. Study Records Retention

The Investigator will maintain adequate study records including the CD-ROM with electronically collected study data, medical records, laboratory reports, ICFs, drug disposition records, safety reports, information regarding participants who discontinued and other pertinent data, such as letters and administrative documents exchanged between the Sponsor and the center. Records can be in paper or electronic format.

All study records must be retained by the Investigator for the maximum period of time authorized by the hospital, institution or clinic but in no case for less than **15 years** after study completion.

To avoid any possible errors, the Investigator must contact the Sponsor prior to the destruction of any study records or if leaving the institution where the study was conducted. The Investigator will notify the Sponsor in the event of accidental loss or destruction of any study records.

11.4. Protocol Deviations

All protocol deviations should be documented.

11.5. Changes in the Conduct of the Study

See Section 13.9.

11.5.1. Public Health Emergencies

In case of a public health emergency, such as pandemics, study procedures might have to be adapted to enhance safety for participants and study personnel, as well as to accommodate WHO and/or local Health Agencies recommendations.

Such adaptations include, but are not limited to, more restrictive eligibility criteria to temporarily exclude participant sub-populations at higher health risk, alternative visit schedules for enrolled participants, study monitoring procedures, alternative supply chain to ensure delivery of medication to participant on treatment, etc.

Such changes will be implemented via separate communication to Investigators and captured in the trial master file.

Unless such changes are to be implemented on a permanent basis for the rest of the study, a protocol amendment will not be issued. Communication to the EC/IRBs and Regulatory Agencies on implementation of these time-limited changes will follow local requirements.

11.6. Publication and Data Sharing Policy

Results of this Phase 3 study will not be publicly disseminated or published until the study data are mature for the analysis of the primary study endpoint (as defined by the protocol). The publications must be conform to the CONSORT guidelines (Schulz et al. 2010).

However, for the purpose of submission of abstracts to congresses, a draft version of the analysis report may be generated if the Sponsor's Statistician determines prior to abstract submission that the inconsistencies remaining in the database will not affect the conclusions of the study, and that the database can be cleaned and locked in sufficient time to enable the preparation of the final statistical report by the time of presentation. In this case, the abstract should clearly stipulate that the results are not definitive.

The publication of the results of ancillary studies (e.g., translational research) is authorized at any time provided they do not mention the primary and secondary study endpoints.

All publications reporting results of this Phase 3 study must be reviewed and approved by the Sponsor's Statistician and Medical Monitor in charge of the study, the first author and the TSC. The first author is responsible for ensuring that all co-authors have seen and approved the final version of the publication prior to submission. A written agreement with the intent to submit a publication must be reached between the Sponsor, the first author and the TSC.

In accordance with the International Committee of Medical Journal Editors (Editors 2010), each author of the publication should have participated sufficiently in the work to take public responsibility for the content. All other contributors (clinicians, pathologists, etc.) who do not meet enough criteria for authorship will be acknowledged in the publication.

For the primary publication, the first author will be a TSC member who will be the primary person responsible for generating the first manuscript draft, followed by the other TSC members. In principle, the last author will be a TSC Chairman (if different from the first author). The Investigators who enrolled evaluable participants in the study will be included as co-authors up to the total number of co-authors allowed by the journal, according to their contribution to participant enrolment.

Coordinators of integrated translational research components of the study or pathologists responsible for the central pathology review that is part of the study also qualify as co-authors. Two Sponsor representatives will be co-authors. These 2 co-authors are usually the Statistician and the Medical Monitor who oversaw and contributed to the study.

All Investigators who enrolled evaluable participants into the study (i.e., clinicians) or contributed scientifically to the study (i.e., pathologists, collaborators from the same institutions, etc.) will be acknowledged in the publication. The acknowledgment list should include the name of all participating institutions and the name of the clinicians and other scientists involved with the study at that institution. Whenever a study participant has moved from one institution to another in the course of the study, that participant is listed with the institution to which he/she was affiliated at the time of starting his/her participation to the study, with the mention "(now at [new affiliation])".

Sponsor staff that made a substantial scientific contribution to the study but are not co-authors should be mentioned in the acknowledgment section (i.e., data managers, clinical scientists, clinical study managers).

The person who took the lead in conducting an ancillary study is the first author of the relevant publication. The Sponsor representatives who contributed to the design, conception, analysis and publication, if any, will also be co-authors. The list of co-authors must be approved by the TSC and Sponsor.

11.7. Insurance Policy

The Sponsor will subscribe a liability insurance covering his and the Investigator's responsibility as well as the responsibility of any person involved in the conduct of the study, provided there is proper adherence to the protocol. An insurance certificate will be provided by the Sponsor to the IEC/IRB if required.

13. APPENDICES

13.1. ECOG Performance Status

Table 13-1 ECOG Performance Status

Grade	ECOG
0	Fully active, able to carry on all pre-disease performance without restriction
1	Restricted in physically strenuous activity but ambulatory and able to carry out work of a light or sedentary nature, e.g., light house work, office work
2	Ambulatory and capable of all self-care but unable to carry out any work activities. Up and about more than 50% of waking hours
3	Capable of only limited self-care, confined to bed or chair more than 50% of waking hours
4	Completely disabled. Cannot carry on any self-care. Totally confined to bed or chair
5	Dead

Source: Oken, M.M., Creech, R.H., Tormey, D.C., Horton, J., Davis, T.E., McFadden, E.T., Carbone, P.P.: *Toxicity And Response Criteria Of The Eastern Cooperative Oncology Group.* Am J Clin Oncol 5:649-655, 1982.

13.2. Cisplatin Administration

Please consult and follow the instructions provided in your local label.

Preparation

Do not use needles or intravenous sets containing aluminum parts that can come in contact with cisplatin for injection during preparation or administration. Aluminum reacts with cisplatin for injection, causing precipitate formation and a loss of potency.

Cisplatin for injection is a cytotoxic drug. Follow applicable special handling and disposable procedures.

Dilution

For preparation of the infusion solution, it is recommended that the solution be further diluted in 1 to 2 L of a compatible infusion solution with or without 37.5 g of mannitol. Refer to detailed references for specific infusion solution stability and compatibility information.

Administration

Administer cisplatin for injection by slow intravenous infusion.

Warnings and Precautions

Nephrotoxicity

Cisplatin for injection can cause dose-related nephrotoxicity, including acute renal failure that becomes more prolonged and severe with repeated courses of the drug. Renal toxicity typically begins during the second week after a dose of cisplatin for injection. Patients with baseline renal impairment, geriatric patients, patients who are taking other nephrotoxic drugs, or patients who are not well hydrated may be more susceptible to nephrotoxicity.

Ensure adequate hydration before, during, and after cisplatin for injection administration (see Appendix 13.3). Measure serum creatinine, blood urea nitrogen, creatinine clearance, and serum electrolytes including magnesium prior to initiating therapy, and as clinically indicated. Consider magnesium supplementation as clinically needed.

Creatinine, eGFR and electrolytes local measurement must take place 48 hours (±12 hours) after cisplatin administration to avoid or mitigate renal toxicities.

Peripheral Neuropathy

Cisplatin for injection can cause dose-related peripheral neuropathy that becomes more severe with repeated courses of the drug. Neurologic symptoms have been reported to occur after a single dose. Neuropathy can also have a delayed onset from 3 to 8 weeks after the last dose of cisplatin for injection. Manifestations include paresthesias in a stocking-glove distribution, areflexia, and loss of proprioception and vibratory sensation. The neuropathy may progress further even after stopping treatment. Peripheral neuropathy may be irreversible in some patients.

Consider permanent discontinuation of cisplatin for injection for patients who develop symptomatic peripheral neuropathy. Geriatric patients may be more susceptible to peripheral neuropathy.

Nausea and vomiting

Cisplatin for injection is a highly emetogenic antineoplastic agent. Premedicate with antiemetic agents. Without antiemetic therapy, marked nausea and vomiting occur in almost all patients treated with cisplatin for injection and may be so severe that the drug must be discontinued. Nausea and vomiting may begin within 1 to 4 hours after treatment and last up to 72 hours. Maximal intensity occurs 48 to 72 hours after administration. Various degrees of vomiting, nausea, and/or anorexia may persist for up to 1 week after treatment. Delayed nausea and vomiting (begins or persists 24 hours or more after chemotherapy) has occurred in patients attaining complete emetic control on the day of cisplatin for injection therapy. Consider the use of additional antiemetics following infusion.

Myelosuppression

Myelosuppression suppression occurs in 25% to 30% of patients treated with cisplatin for injection. Fever and infection have been reported in patients with neutropenia. Potential fatalities due to infection (secondary to myelosuppression) have been reported. Geriatric patients may be more susceptible to myelosuppression.

Perform standard hematologic tests before initiating cisplatin for injection, before each subsequent course, and as clinically indicated. Closely monitor participants for the development of signs and symptoms of infection during and after treatment with cisplatin for injection. For participants who

develop severe myelosuppression during treatment with cisplatin for injection, consider dose modifications and manage according to clinical treatment guidelines.

Hypersensitivity reactions

Cisplatin for injection can cause severe hypersensitivity reactions, including anaphylaxis and death. Manifestations have included facial edema, wheezing, tachycardia, and hypotension. Hypersensitivity reactions have occurred within minutes of administration to patients with prior exposure to cisplatin for injection.

Monitor participants receiving cisplatin for injection for possible hypersensitivity reactions. Ensure supportive equipment and medications are available to treat severe hypersensitivity reactions. Severe hypersensitivity reactions require immediate discontinuation of cisplatin for injection and aggressive therapy. Participants with a history of severe hypersensitivity reactions should not be rechallenged with cisplatin for injection. Cross-reactivity between platinum-based antineoplastic agents has been reported. Cases of severe hypersensitivity reactions have recurred after rechallenging patients with a different platinum agent.

Ototoxicity

Cisplatin for injection can cause ototoxicity, which is cumulative and may be severe. Consider audiometric and vestibular function monitoring.

Ototoxicity is manifested by tinnitus, hearing loss in the high-frequency range (4,000 to 8,000 Hz) and/or decreased ability to hear normal conversational tones. Ototoxicity can occur during or after treatment and can be unilateral or bilateral. Deafness after the initial dose of cisplatin for injection has been reported. Vestibular toxicity has also been reported.

Ototoxic effects can be more severe and detrimental in pediatric patients, particularly in patients less than 5 years of age. The prevalence of hearing loss in pediatric patients is estimated to be 40-60%. Additional risk factors for ototoxicity include simultaneous cranial irradiation, treatment with other ototoxic drugs and renal impairment. Consider audiometric and vestibular testing in all pediatric patients receiving cisplatin.

Genetic factors (e.g., variants in the thiopurine S-methyltransferase [TPMT] gene) may also contribute to the cisplatin-induced ototoxicity; although this association has not been consistent across populations and study designs.

Ocular toxicity

Optic neuritis, papilledema, and cortical blindness have been reported in patients receiving standard recommended doses of cisplatin for injection. Blurred vision and altered color perception have been reported after the use of regimens with higher doses and dose frequencies of cisplatin for injection. The altered color perception manifests as a loss of color discrimination, particularly in the blue-yellow axis and irregular retinal pigmentation of the macular area on fundoscopic exam. Improvement and/or total recovery usually occurs after discontinuing cisplatin for injection but can be delayed.

Secondary malignancies

The development of acute leukemia secondary to the use of cisplatin for injection has been reported. In these reports, cisplatin for injection was generally given in combination with other leukemogenic agents.

Embryo-fetal toxicity

Based on human data, cisplatin for injection can cause fetal harm when administered to a pregnant woman. Advise pregnant women and females of reproductive potential of the potential risk to a fetus. Advise females of reproductive potential to use effective contraception during treatment and for 14 months after the last dose of cisplatin for injection. Advise male participants with female partners of reproductive potential to use effective contraception during treatment and for 11 months after the last dose of cisplatin for injection.

Injection site reactions

Injection site reactions can occur during the administration of cisplatin for injection. Local soft tissue toxicity has been reported following extravasation of cisplatin for injection. Severity of the local tissue toxicity appears to be related to the concentration of the cisplatin for injection solution. Infusion of solutions with a cisplatin for injection concentration greater than 0.5 mg/mL may result in tissue cellulitis, fibrosis, necrosis, pain, edema, and erythema.

Because of the possibility of extravasation, closely monitor the infusion site during drug administration.

13.3. Cisplatin Hydration Guidelines

Adequate hydration must be maintained from 2 to 12 hours prior to administration until minimum 6 hours after the administration of cisplatin (SmPC TEVA v6.0 2019).

Hydration is necessary to cause sufficient diuresis during and after treatment with cisplatin. It is realized by intravenous infusion of one of the following solutions:

- Sodium chloride solution 0.9%
- Mixture of sodium chloride solution 0.9% and glucose solution 5% (1:1).

Hydration prior to treatment with cisplatin:

• Intravenous infusion of 100 to 200 ml/hour for a period of 6 to 12 hours, with a total amount of at least 1 L.

Hydration after termination of the administration of cisplatin:

 Intravenous infusion of another 2 liters at a rate of 100 to 200 ml per hour for a period of 6 to 12 hours.

Forced diuresis may be required should the urine secretion be less than 100 to 200 ml/hour after hydration. Forced diuresis may be realized by intravenously administering 37.5 g mannitol as a 10% solution (375 ml mannitol solution 10%), or by administration of a diuretic if the kidney functions are normal. The administration of mannitol or a diuretic is also required when the administrated cisplatin dose is higher than 60 mg/m² of body surface.

It is necessary that the participant drinks large quantities of liquids for 24 hours after the cisplatin infusion to ensure adequate urine secretion.

Hydration guidelines may be modified at the discretion of the treating physician provided adequate pre and post cisplatin hydration is achieved, and renal function remains adequate.

Consider a more extensive hydration regimen under certain circumstances:

Additional pre hydration with normal saline iv or orally at minimum in the 48 hours preceding cisplatin infusion and a more extensive post-hydration regimen is requested whenever possible in those patients with risk factors for renal toxicity, e.g., proteinuria, diabetes, and hypertension.

The patient's hydration status is requested to be reviewed whenever a patient's renal lab is worsening during the study, with a mandatory review on Day 4. Attention should also be paid to any signs of dehydration (insufficient urine outputs) or conditions leading to a potential dehydration like diarrhea, vomiting, undernutrition, infection/fever.

In case of inadequate hydration status and worsening renal lab, additional iv hydration is requested whenever possible until renal lab improves.

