The End of treatment (EOT) visit will be performed 15 days (± 7days) after last study treatment administration (i.e., xevinapant/placebo, chemotherapy or IMRT whichever is administered last), but prior to the start of any subsequent anticancer therapy (see also Section 7.1).

Study procedures must be performed according to the planned visit schedule within the permitted visit windows. During the treatment period, each study visit day and allowed time windows will be based on the C1D1 date. The treatment diagram and time windows for visits during the treatment period are presented in Table 1-2.

NOTE: Renal function monitoring must also take place 48 hours (± 12 hours) after cisplatin infusion (i.e. at C1D4, C2D4, C3D4) based on local laboratory assessments as shown below (see also Table 1-1):

Local Laboratory Sampling	Schedule for Renal Function Monitoring
Creatinine, eGFR Sodium, potassium, calcium, magnesium	C1D4 (within 48±12 hours from C1D2)
Codam, potassiam, calcium, magnesiam	C2D4 (within 48±12 hours from C2D2)
	C3D4 (within 48±12 hours from C3D2)

In case of abnormal renal function parameter(s) or electrolyte disbalance, additional hydration and electrolyte replacement should be considered, as well as cisplatin dose adaptation in the next cycle.

Adequate hydration must be maintained pre- and post-cisplatin infusion according to the following schedule (see Appendix 13.3 for detailed instructions):

Pre-infusion	Post-infusion
2 to 12 hours prior to administration of cisplatin	until minimum 6 hours after the administration of cisplatin

Every attempt should be made to have each participant attend each visit as scheduled. Study visits/procedures performed outside of the allowed visit window will be considered as protocol deviations, with the exception of premature discontinuation from study treatment or withdrawal from the study due to reasons described in Section 7.

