6.1.2.2. Chemotherapy

All participants will receive high-dose cisplatin (100 mg/m²) intravenously over at least 90 minutes on Day 2 Q3W up to a maximum of 3 cycles in total (see administration schedule in Table 1-1 and Table 1-2). If body surface area is >2.00 m², total administered dose will be capped at a maximum of 200 mg. Please consult and follow cisplatin administration instructions provided in your local label. The infusion has to be administered with pre- and post-infusion hydration +/- mannitol and/or diuretics, according to institutional guidelines. Any pre-existing dehydration should be corrected. Please refer to Appendices 13.2 and 13.3 for additional information on cisplatin administration and suggested hydration regimen.

eGFR (using the CKD-EPI creatinine formula) should be ≥60 mL/min/1.73m² before administration of cisplatin at C1D2; re-treatment conditions as specified in Table 6-1 should be met.

Participants should receive at least one dose of cisplatin on C1D2.

Standard antiemetic prophylaxis for high-dose cisplatin containing regimens are mandatory starting on Day 1 of each chemotherapy containing cycle. Standard antiemetics guidelines (administration of pre- and post-treatment 5-HT3 receptor antagonists, neurokinin-1 receptor antagonists and dexamethasone [or any other corticosteroid at equivalent dose i.v.] according to the 2016 MASCC and ESMO guideline (Roila et al. 2016)]) are provided in Section 6.5.1; however the specifics of the regimen are at the discretion of the treating physician, provided adequate control is achieved.

Note: Dose and schedule of dexamethasone coupled with its wide availability in various forms established it as the agent of choice in the 2016 MASCC and ESMO guideline. If an equivalent dose of corticosteroids is used according to institutional guidelines, the risk of increased toxicity to corticosteroids should be carefully monitored. Elevations of plasma levels may be triggered by xevinapant inhibition of CYP3A4.

The participant can switch to carboplatin in C2 and/or C3 as per the dose modifications outlined in Table 6-1 (NCCN Chemotherapy Order Templates 2020). Please consult and follow the carboplatin administration instructions provided in your local label.

No pre- or post-treatment hydration or forced diuresis is required for carboplatin administration.

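### Protocol 13.3: the 2 L post-cisplatin volume fits only a small part of the stated rate and duration ranges, and the pre-hydration lower bound is 2 h in two places but 6 h in a third

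*Protocol*

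**What the plan says.** **After cisplatin.** Protocol 13.3 gives one instruction with three linked quantities: "Intravenous infusion of another 2 liters at a rate of 100 to 200 ml per hour for a period of 6 to 12 hours". The table in Protocol 1.3 gives no volume or rate, only an end point: "until minimum 6 hours after the administration of cisplatin".

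**Before cisplatin.** The regimen bullet in 13.3 reads "Intravenous infusion of 100 to 200 ml/hour for a period of 6 to 12 hours, with a total amount of at least 1 L". The opening sentence of the same appendix reads "Adequate hydration must be maintained from 2 to 12 hours prior to administration until minimum 6 hours after the administration of cisplatin". The Section 1.3 table has the same lower bound as that sentence: "2 to 12 hours prior to administration of cisplatin".

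**Status of the text.** Section 1.3 makes its schedule mandatory and sends the reader to the appendix: "Adequate hydration must be maintained pre- and post-cisplatin infusion according to the following schedule (see Appendix 13.3 for detailed instructions". Section 6.1.2.2 is softer. It refers to institutional guidelines for hydration and then says: "Please refer to Appendices 13.2 and 13.3 for additional information on cisplatin administration and suggested hydration regimen". Appendix 13.3 itself allows departures while hydration and renal function are adequate: "Hydration guidelines may be modified at the discretion of the treating physician provided adequate pre and post cisplatin hydration is achieved, and renal function remains" (last word of the sentence omitted).

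The SAP sets no hydration figures. Its Section 13 only plans to tabulate, by cycle, the cisplatin-treated participants who had pre- and post-infusion hydration.

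**The concern.** A volume, a rate and a duration stated together over-determine an infusion: any two fix the third. If the ranges do not agree, a site that picks a duration and a rate from inside the stated limits will usually miss the stated volume, and a site that gives the volume will usually have to leave the rate or duration limits. For pre-hydration, a site working from the Section 1.3 schedule and a site working from the 13.3 bullet would plan different lead times.

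All participants are to receive high-dose cisplatin. Appendix 13.2 warns of dose-related nephrotoxicity and lists poor hydration among the factors that raise susceptibility. The sponsor has already acted on this subject: the amendment history records that version 9.0 added the 48 h renal check and version 10.0 extended 13.3. Acute renal failure is in the SAP's legacy AESI list (SAP Appendix 2). What is at stake is the clarity of a safety instruction that applies to both arms, not the treatment comparison.

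**Working it through.** **Inputs (Protocol 13.3 and 1.3).** Post-cisplatin volume V = 2000 ml, rate r = 100-200 ml/h, duration t = 6-12 h. Pre-cisplatin infusion in the bullet: 6-12 h. Pre-cisplatin lead time in the opening sentence of 13.3 and in Section 1.3: 2-12 h.

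**1. Post-hydration: what the stated limits deliver.** Volume = r × t.

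| Rate | 6 h | 12 h |
|---|---|---|
| 100 ml/h | 600 ml | 1200 ml |
| 200 ml/h | 1200 ml | 2400 ml |

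Only the corner with both the highest rate and the longest duration exceeds 2 L. The stated 2 L is therefore not reproduced over the stated ranges as a whole.

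**2. Time and rate needed for 2 L.**
- At 200 ml/h: 2000 / 200 = 10 h.
- At 100 ml/h: 2000 / 100 = 20 h, beyond the 12 h limit.
- In 12 h: 2000 / 12 = 167 ml/h.
- In 6 h: 2000 / 6 = 333 ml/h, above the 200 ml/h limit.

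So 2 L needs a rate of about 167-200 ml/h together with a duration of 10-12 h. Durations from 6 h to just under 10 h (two-thirds of the stated range) cannot deliver it at any stated rate. Rates below about 167 ml/h (also two-thirds of the range) cannot deliver it at any stated duration.

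**3. Share of the rate-by-duration range that reaches 2 L.** The range has area (200 − 100) × (12 − 6) = 600. The area with r × t ≥ 2000 is the integral of (12 − 2000/r) for r from 166.7 to 200:

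12 × (200 − 166.7) − 2000 × ln(200/166.7) = 400 − 364.6 = 35.4

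35.4 / 600 = 5.9%. A numerical grid gives the same figure. About 94% of the range falls short. This describes how the stated limits fit together; it is not an estimate of what sites do.

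**4. The 6 h minimum.** The post-infusion minimum in Section 1.3 equals the shortest duration in the bullet. At 6 h the most that the stated rates allow is 200 × 6 = 1200 ml, which is 60% of 2 L.

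**5. Pre-hydration window, side by side.**

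| Place | Lower bound | Upper bound |
|---|---|---|
| Section 1.3 table | 2 h before | 12 h before |
| 13.3, opening sentence | 2 h before | 12 h before |
| 13.3, regimen bullet | 6 h infusion | 12 h infusion |

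The upper bounds agree. A start 2 h before cisplatin, or at any time up to just under 6 h before, satisfies the first two places but cannot contain even the shortest infusion in the third. The conflict lies inside 13.3 (opening sentence against bullet) and between Section 1.3 and that bullet. Section 1.3 and the opening sentence of 13.3 agree with each other.

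**The case against.** The strongest case is that the text can be satisfied and is heavily safeguarded. Volume, rate and time are joint conditions in one sentence, so a site giving 0.6-1.2 L has not followed it, and a compliant combination exists. Ranges given with a target volume need not work at every corner. Section 6.1.2.2 defers to institutional guidelines and the local label and calls 13.3 a suggestion. The treating physician may modify the regimen. Appendix 13.3 also requires mannitol or a diuretic above 60 mg/m² (the planned dose is 100 mg/m²), asks for high oral intake for 24 h, mandates a hydration review on Day 4 and asks for extra i.v. fluid if renal laboratory values worsen. Section 1.3 requires a renal check 48 h (±12 h) after each cisplatin infusion.

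Much of this stands. It rules out three stronger inferences that a reader might draw:

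- **That the pre-hydration rate and time conflict with the 1 L total.** A reader might multiply 100 ml/h by 6 h, get 0.6 L and call it an error. The bullet carries its own 1 L floor, which excludes that combination, and about 82% of its rate-by-duration range meets the floor. This is an ordinary range with a minimum.
- **That the protocol permits 0.2-0.4 L before cisplatin.** That figure joins the 2 h lead time from one sentence to the rate from another. Nothing in the protocol prescribes 100-200 ml/h for 2 h.
- **That renal protection is left undefined.** The safeguards above are explicit and do not depend on the conflicting figures.

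The objection does not make the figures agree. Two-thirds of the stated post-infusion durations cannot deliver the stated volume at any stated rate, which is more than an awkward corner. The discretion clause depends on hydration being adequate, and the only volumes, rates and times offered for judging that are the ones in conflict. Treating the detailed bullet as controlling does not settle the pre-hydration window either, because the opening sentence of the same appendix contradicts it.

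**Conclusion.** The point holds as two inconsistencies in the protocol's own figures. First, the post-cisplatin volume of 2 L is compatible with the stated rate and duration only at about 167-200 ml/h for 10-12 h, and the 6 h duration reaches at most 1.2 L. Second, the pre-hydration lower bound is 2 h in the opening sentence of 13.3 and in the mandatory Section 1.3 schedule, but 6 h in the 13.3 bullet.

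The practical effect is limited by the status of 13.3 as a suggestion, by institutional guidelines and physician discretion, and by the other renal safeguards. The text applies to both arms, and no effect on endpoints, power, type I error or the treatment comparison is claimed. Nothing in the documents shows that any participant was under-hydrated.

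The arithmetic assumes a constant rate within the stated limits and counts only the post-infusion fluid described in that bullet, not the 1 to 2 L in which Appendix 13.2 recommends diluting the cisplatin. Appendix 13.3 cites a product label that is not available here, so whether the figures reproduce that label, and which of them is out of line, cannot be judged.

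**What to change.** In Protocol 13.3, reconcile the post-cisplatin volume, rate and duration so that the three statements agree. Reconcile the pre-hydration window between the opening sentence and the regimen bullet of 13.3, and carry the result into the Section 1.3 table. While doing so, align the mandatory wording in Section 1.3 with the description of 13.3 in Section 6.1.2.2 as a suggestion, so that sites know which parts bind them. The sponsor sets the clinical values; none is proposed here.

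The cost is protocol wording and a notice to sites. No analysis, sample size or SAP change is needed. The hydration tabulation in SAP Section 13 can stay as it is and will be easier to interpret once the instruction is consistent.
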